10.3 Database management and quality control

Novartis (or a designated CRO) will review the data entered into the CRFs by investigational staff for completeness and accuracy and instruct the site personnel to make any required corrections or additions. Queries are sent to the investigational site using an electronic data query. Designated investigator site staff are required to respond to the query and confirm or correct the data. If the electronic query system is not used, a paper Data Query Form will be faxed to the site. Site personnel will complete and sign the faxed copy and fax it back to Novartis (or a designated CRO) who will make the correction to the database. The signed copy of the Data Query Form is kept at the investigator site.

Concomitant medications entered into the database will be coded using the WHO Drug Reference List, which employs the Anatomical Therapeutic Chemical classification system. Medical history/current medical conditions and adverse events will be coded using the Medical dictionary for regulatory activities (MedDRA) terminology.

Laboratory samples will be processed centrally and the results will be sent electronically to Novartis (or a designated CRO).

Randomization codes will be tracked using an Interactive Response Technology (IRT). The system will be supplied by a vendor, who will also manage the database. The database will be sent electronically to Novartis (or a designated CRO).

Each occurrence of a code break via IRT will be reported to the clinical team and monitor. The code break functionality will remain available until study shut down or upon request of Novartis.

The occurrence of any protocol deviations will be determined. After these actions have been completed and the database has been declared to be complete and accurate, it will be locked and the treatment codes will be unblinded and made available for data analysis. Any changes to the database after that time can only be made by joint written agreement between the COAR Analytics NIBR Franchise Head and the relevant NIBR TA Head.

Corporate Confidential Information

10.4 Data Monitoring Committee

Not required.

10.5 Adjudication Committee

Not required.

11 Data analysis

The analysis will be conducted on all patient data at the time the trial ends. Any data analysis carried out independently by the investigator should be submitted to Novartis before publication or presentation.

11.1 Analysis sets

For all analysis sets, patients will be analyzed according to the study treatment received.

The safety analysis set will include all patients that received any study drug.

The PK analysis set will include all patients with at least one available valid (i.e. not flagged for exclusion) PK concentration measurement, who received any study drug and with no protocol deviations that impact on PK data.

The PD analysis set will include all patients with available PD data and no protocol deviations with relevant impact on PD data.

11.2 Patient demographics and other baseline characteristics

All data for background and demographic variables will be listed by treatment group and patient. Summary statistics will be provided by treatment group.

Relevant medical history, current medical conditions, results of laboratory screens and any other relevant information will be listed by treatment group and patient.

11.3 Treatments

Data for study drug administration (rescue medication) and concomitant therapies will be listed by treatment group and patient.

11.4 Analysis of the primary variable(s)

The primary objective of this study is to assess the safety and tolerability of LMB763 as well as the efficacy of LMB763 on ALT in NASH patients during 12 weeks of treatment. Safety/tolerability data will be summarized. Further details are provided in [Section 11.4.4](#).

11.4.1 Variable(s)

Change from baseline to Week 12 in ALT is the primary efficacy variable. 'Baseline' is defined as the mean of ALT levels at baseline (V2) and pre-dose (V101) visits.

11.4.2 Statistical model, hypothesis, and method of analysis

A Bayesian approach will be used to analyze the change from baseline to Week 12 in ALT, which is assumed to follow a normal distribution with a known variance for each treatment arm. An informative prior for the placebo treatment effect and a non-informative prior for the LMB763 treatment effect will be incorporated into the analysis. The variance and the informative prior will be based on historical control data from studies such as the FLINT trial ([Neuschwander-Tetri et al 2015](#)). Median estimates, credible intervals and posterior probabilities that the placebo-adjusted ALT reduction by an LMB763 dose is (a) greater than 0 and (b) greater than 19 U/L and/or another cutoff value will be provided within the Bayesian framework. As a sensitivity analysis, the posterior probabilities will be calculated for varying values of the effective sample size for the placebo prior. A further sensitivity analysis using different values of the common variance assumed in the likelihood function and the prior may be performed as needed. An analysis using SAS PROC MCMC without assuming the variance is known in the likelihood function may be performed as well.

Additionally a repeated measures analysis of covariance (ANCOVA) will be performed for change from baseline ALT without using historical placebo control data. The model will include effects for treatment, visit, treatment by visit interaction, stratification factor (BMI group), baseline, and baseline by visit interaction. An unstructured variance-covariance structure will be used to account for correlation among multiple measurements from the same patient and variance heterogeneity. Point estimates, the associated two-sided 90% confidence intervals as well as the p-values for treatment differences will be obtained. The null hypothesis of no treatment difference will be tested at the one-sided 0.05 significance level. Both untransformed and log-transformed ALT will be analyzed. For log-transformed ALT analysis the ratio to baseline results obtained by back transformation will be reported

The cohort effect will be explored and a cohort-wise analysis for both the Bayesian and ANCOVA approaches may be performed as needed.

If placebo data from in-house studies in a similar patient population become available they may be included in an ANCOVA on log-transformed data via informative priors.

11.4.3 Handling of missing values/censoring/discontinuations

Assuming missing at random, a patient with missing value at a visit will still contribute to the estimation of the treatment effect at that particular visit as the likelihood-based repeated measures ANCOVA borrows information from non-missing values of this patient and other patients.

11.4.4 Summary statistics of safety

Vital signs

All vital signs data will be listed by treatment group, patient, and visit/time and if ranges are available abnormalities (and relevant orthostatic changes) will be flagged. Summary statistics will be provided by treatment and visit/time.

ECG evaluations

All ECG data will be listed by treatment group, patient and visit/time, abnormalities will be flagged. Summary statistics will be provided by treatment and visit/time.

Clinical laboratory evaluations

All laboratory data will be listed by treatment group, patient, and visit/time and if normal ranges are available abnormalities will be flagged. Summary statistics will be provided by treatment and visit/time.

Adverse events

All information obtained on adverse events will be displayed by treatment group and patient.

The number and percentage of patients with adverse events will be tabulated by body system and preferred term with a breakdown by treatment. A patient with multiple adverse events within a body system is only counted once towards the total of this body system.

Other safety evaluations

Not applicable.

11.4.5 Sensitivity analyses

If more than 10% of the data for the Bayesian analysis on the change from baseline to Week 12 in ALT are missing then the Last Observation Carried Forward (LOCF) approach and/or another method may be used to impute missing data and the Bayesian analysis re-conducted.

11.5 Analysis of secondary variable(s)

11.5.1 Efficacy / Pharmacodynamics

Log-transformed ratio to baseline % liver fat and fasting lipid profiles (total cholesterol, HDL, LDL, triglycerides) as well as change from baseline % liver fat, weight, BMI, WTH ratio will be analyzed using the same repeated measures ANCOVA described in [Section 11.4.2](#) with

log-transformed baseline in lieu of baseline as a covariate for lipid parameters. Fibroscan[®] (in a subset of patients), ELF and fibrosis biomarker test data will be analyzed similarly and the log-transformation applied prior to the analysis as needed. For parameters with only one post-treatment measurement an ANCOVA with treatment as a classification factor and baseline (or log-transformed baseline if applicable) as a covariate will be employed. For % liver fat, if historical placebo control data in a similar patient population are identified in the literature or become available from in-house studies later on then they may be incorporated into a Bayesian analysis as described for ALT.

11.5.2 Pharmacokinetics

LMB763 plasma concentration data will be listed by patient and visit/sampling time point. Descriptive summary statistics will be provided by visit/sampling time point, including the frequency (n, %) of concentrations below the LLOQ and reported as zero.

Summary statistics will include mean (arithmetic and geometric), SD, CV (arithmetic and geometric), median, minimum and maximum. An exception to this is Tmax where median, minimum and maximum will be presented. Concentrations below LLOQ will be treated as zero in summary statistics and for PK parameter calculations. A geometric mean will not be reported if the dataset includes zero values. Pharmacokinetic parameters will be calculated as described in [Section 8.7](#) and will be listed by patient.

For standard pharmacokinetic abbreviations and definitions see the list provided at the beginning of this protocol.

The following pharmacokinetic parameters will be determined using the actual recorded sampling times and non-compartmental method(s) with Phoenix WinNonlin (Version 6.2 or higher): Cmax, Tmax, AUClast, AUCtau, Racc, T1/2, Vz/F and CL/F from the plasma concentration-time data. The linear trapezoidal rule will be used for AUC calculation. Regression analysis of the terminal plasma elimination phase for the determination of T1/2 will include at least 3 data points after Cmax. If the adjusted R² value of the regression analysis of the terminal phase is less than 0.75, no values will be reported for T1/2, AUCinf and CL/F.

An assessment of dose proportionality of LMB763 exposure will be conducted using Cmax and AUC. An Analysis of Variance (ANOVA) with dose as the classification factor will be performed on log-transformed dose-normalized parameters. A comparison between the 2 doses will be made within the ANOVA framework. The ratio of geometric means and the associated 90% confidence interval (CI) will be obtained by back-transforming the least squares mean treatment difference and the corresponding 90% CI in the log domain to the original scale.

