IEC	Independent Ethics Committee
IRB	Institutional Review Board
IRT	Interactive Response Technology
LDH	lactate dehydrogenase

LFT	Liver function test
LLN	lower limit of normal
LLQ	lower limit of quantification
MedDRA	Medical dictionary for regulatory activities
mg	milligram(s)
mL	milliliter(s)
MRI	Magnetic resonance imaging
NASH	Non-alcoholic steatohepatitis
NCDS	Novartis Clinical Data Standards
o.d.	once a day
p.o.	Oral
PA	posteroanterior
PD	pharmacodynamic(s)
PK	pharmacokinetic(s)
RBC	red blood cell(s)
RDC	Remote Data Capture
REB	Research Ethics Board
SAE	serious adverse event
sCR	serum creatinine
SD	standard deviation
SGOT	serum glutamic oxaloacetic transaminase
SGPT	serum glutamic pyruvic transaminase
SOM	Site Operations Manual
SUSAR	Suspected Unexpected Serious Adverse Reactions
TBL	total bilirubin
ULN	upper limit of normal
ULQ	upper limit of quantification
WBC	white blood cell(s)
WHO	World Health Organization
WTH	Waist to hip

Pharmacokinetic definitions and symbols

AUC _{last}	The area under the plasma (or serum or blood) concentration-time curve from time zero to the time of the last quantifiable concentration [mass x time / volume]
AUC _{tau}	The area under the plasma (or serum or blood) concentration-time curve from time zero to the end of the dosing interval tau [mass x time / volume]
CL/F	The apparent systemic (or total body) clearance from plasma (or serum or blood) following extravascular administration [volume / time]
C _{max}	The observed maximum plasma (or serum or blood) concentration following drug administration [mass / volume]
R _{acc}	The accumulation ratio
T _{1/2,acc}	The effective half-life based on drug accumulation at steady state [time]
T _{max}	The time to reach the maximum concentration after drug administration [time]
V _{z/F}	The apparent volume of distribution during the terminal elimination phase following extravascular administration [volume]

Glossary of terms

Assessment	A procedure used to generate data required by the study
Cohort	A specific group of subjects fulfilling certain criteria
Control drug	Any drug (an active drug or an inactive drug, such as a placebo) which is used as a comparator to the investigational drug being tested in the trial
Dosage	Dose of the study treatment given to the subject in a time unit (e.g. 100 mg once a day, 75 mg twice a day)

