The study will consist of a 45 day screening period (Day -60 to Day -21), a baseline period of 20 days (Day -20 to Day -1), a treatment period of 12 weeks (Day 1 to Day 84), and a study completion evaluation approximately twenty-eight days after the last drug administration (Day 112 +/- 2 days). Patients will be advised to maintain their recommended diet for NASH during the study. The study design scheme is shown below.

Figure 3-2 Study design – Cohort 2

- ^a Patients will be randomized in a 2:1 ratio to receive LMB763 (n ~ 64) or matching Placebo (n ~ 32). Study medication will be self administered by patients once daily for 12 weeks. On visit days, study medication will be administered at the site.
- ^b EOS evaluation to be completed approximately 28 days after the final study drug administration (i.e. Day 112 (± 2 days))
- ^c Treatment randomization may occur prior to day 1 as soon as patient eligibility is confirmed from baseline assessments
- ^d All visit during the treatment and follow-up periods will have a window of ± 2 days

Cohort 1 and 2

For both cohorts 1 and 2, patients who meet the eligibility criteria at screening will have baseline assessments performed, including determination of the percent liver fat content by MRI.

Randomization will be stratified by BMI at baseline (refer to [Section 6.3](#)).

The Patient's race will be based on the race which the patient self-reports as captured on the demography eCRF.

The first dose of study medication (LMB763 / Placebo) will be administered to patients under fasted conditions on Day 1, following which scheduled assessments will be performed for 6 hours post-dose. A meal will be provided at approximately 4 hours post dose.

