4.2 Exclusion criteria

Cohorts 1 and 2

Patients with NASH phenotype fulfilling any of the following criteria are not eligible for inclusion in this study:

1. History of severe hypersensitivity to drugs of any kind or sensitivity to those including pyrazole (eg celecoxib or stanozolol) or an imidazole ring (eg antifungals including ketoconazole, anthelmintics including mebendazole and nitroimidazole antibiotics including metronidazole).
2. Use of other investigational drugs within 5 half-lives of enrollment, or within 30 days whichever is longer; or longer if required by local regulations.
3. Current use of obeticholic acid (OCA).
4. New initiation GLP-1 agonists such as liraglutide, exenatide, lixisenatide, albiglutide or dulaglutide or DPP4 inhibitors such as sitagliptin, vildagliptin, saxagliptin or linagliptin within 3 months of screening.
5. Patients taking medications prohibited by the protocol. See [Section 5.2](#) for further details.
6. Patients on treatment with the following medicines UNLESS they are on a stable dose for at least 1 month before randomization: insulin (no more than 25% change in dose), beta-blockers, thiazide diuretics, fibrates, statins, niacin, ezetimibe, vitamin E (if doses > 200 IU/day; doses > 800 IU/day are prohibited), thyroid hormone, psychotropic medications, estrogen or estrogen containing birth control. For oral anti-diabetic medications, no more than one step-up or step-down in local prescribing guidelines will be allowed.
7. History of treated or untreated malignancy of any organ system, other than localized basal cell carcinoma of the skin or treated cervical intraepithelial neoplasia, within the past 5 years, regardless of whether there is evidence of local recurrence or metastases.
8. Pregnant or nursing (lactating) women, where pregnancy is defined as the state of a female after conception and until the termination of gestation, confirmed by a positive hCG laboratory test.

9. Women of child-bearing potential, defined as all women physiologically capable of becoming pregnant, unless they are using highly effective methods of contraception during dosing and for 5 days (approximately 5 times the terminal half life) after stopping study medication. **Highly effective contraception methods include:**

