8.1 Assessment schedule

Assessment Schedule

EPOCH	SCREENING		Treatment															
	Visit Name	Screening	Baseline ²⁵	Treatment														
Visit Numbers ¹	1	2	101					102 ³	103 ³	104 ³	105					106 ³	107 ³	199
Study Day(s)	-60 to -15	-14/-20 to -1	1					7 -2 +2	14 -2 +2	28 -2 +2	42 -2 +2					56 -2 +2	84 -2 +2	112 -2 +2
Time (post-dose)	-	-	0h ³	1h	2h	4h ⁴	6h	-	-	-	0h ³	1h	2h	4h ⁴	6h	-	-	-
Informed consent ⁵	X																	
Corporate Confidential Information	X																	
Inclusion / Exclusion criteria	X	X																
Medical history/current medical conditions	X	X																
Demography	X																	
Alcohol Test and Drug Screen	X	X																
Hepatitis and HIV Screen	X																	
Pregnancy test ⁷	X	X	X							X						X	X	X
Physical examination	X	X								X						X	X	X
Body height	X																	
Body weight	X	X								X	X					X	X	X
Waist and Hip circumference	X	X								X	X					X	X	X
Body temperature	X	X														X	X	X
Blood Pressure and Pulse Rate ^{8,9}	X	X							X	X						X	X	X
ECG evaluation	X	X	X	X	X	X	X	X	X	X	X	X	X	X	X	X	X	X
Hematology	X	X	X					X	X	X	X					X	X	X
Blood chemistry	X	X	X					X	X	X	X					X	X	X

¹ Visit structure given for internal programming purpose only

² If a patient withdraws from the study, or if study medication is discontinued for any reason, the patient should be scheduled for a subsequent visit at which time all assessments at the EOS visit should be performed.

³ Assessments to be performed pre-dose

⁴ A meal will be provided 4 hours post dose.

⁵ Informed consent must be provided by all patients before any screening procedures are performed. The pharmacogenetic assessment is optional and requires a separate informed consent to be signed

Corporate Confidential Information

⁷ Serum pregnancy tests will be performed at Screening and end of study; urine tests may be used at other timepoints.

⁸ At screening and baseline, if vital signs are out-of-range, the investigator may obtain two additional readings, so that up to three (3) consecutive assessments are made, each after at least 30 minutes, and with the patient seated quietly during the five (5) minutes preceding the assessment. At least the last reading must be within the ranges provided in order for patients to qualify.

⁹ Blood pressure and pulse rate will be measured in a sitting position at all visits.

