8.7 Pharmacokinetics

PK samples will be collected at the timepoints defined in the [Assessment schedule, Section 8.1](#). Follow instructions outlined in the central laboratory manual regarding sample collection, numbering, processing and shipment. See [Section 8.9](#) regarding the potential use of residual samples.

Corporate Confidential Information

Concentrations will be expressed in mass per volume units. Concentrations below the LLOQ will be reported as “zero” and missing data will be labeled as such in the Bioanalytical Data Report.

Corporate Confidential Information

9 Safety monitoring

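### Terminal T1/2 and Vz/F cannot be estimated reliably on the visible 0 to 6 h schedule, and the adjusted R² rule withholds the wrong parameters

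*Protocol*

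**What the plan says.** Protocol 11.5.2 lists Cmax, Tmax, AUClast, AUCtau, Racc, T1/2, Vz/F and CL/F, all by non-compartmental methods; SAP 5.1 repeats the list. For the half-life, "Regression analysis of the terminal plasma elimination phase for the determination of T1/2 will include at least 3 data points after Cmax". When that fit has an adjusted R² below 0.75, "no values will be reported for T1/2, AUCinf and CL/F". Vz/F is not named in this rule, and AUCinf is not in the parameter list.

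Protocol 8.7 states that "PK samples will be collected at the timepoints defined in the" assessment schedule. The visible time columns in Section 8.1 are 0, 1, 2, 4 and 6 h on Day 1 and again on Day 42, with 0 h marked as pre-dose. Section 3.1 describes Day 1 dosing, "following which scheduled assessments will be performed for 6 hours post-dose". The PK row, most of footnotes 11 to 21 and part of Section 8.7 are redacted.

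The only visible information on half-life is in exclusion criterion 9 (Section 4.2), which requires "contraception during dosing and for 5 days (approximately 5 times the terminal half life) after stopping study medication".

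The PK definitions at the front of the protocol contain neither a terminal T1/2 nor AUCinf. They do contain T1/2,acc: "The effective half-life based on drug accumulation at steady state". Neither Protocol 11.5.2 nor SAP 5.1 lists T1/2,acc.

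SAP 5.3 analyses Day 1 and Day 42 AUC for dose proportionality without saying which AUC.

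**The concern.** A terminal slope needs observations over a reasonable part of the elimination phase. On the visible schedule the profile covers 6 h of a half-life of about 24 h, a quarter of one half-life. The three-point requirement and the R² rule then decide which patients contribute. The R² rule favours profiles that look steep, so the reported values come from a selected subset. Vz/F is calculated by dividing by the same slope, yet it may still be reported when the fit has been rejected.

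Evaluation of PK is the first-listed secondary objective (Protocol 2.2). At stake are the reported half-life and volume, and any Day 1 AUCtau used for accumulation or dose proportionality. The ALT and safety analyses are not affected.

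**Working it through.** The documents give no half-life in hours and no PK calculation, so there is no stated figure to reproduce.

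**Inputs from the documents**
- Half-life: 5 × 24 h / 5 = about 24 h (Section 4.2).
- Sampling grid: 0, 1, 2, 4, 6 h (Section 8.1).
- Dosing interval: 24 h, once daily (Section 6.5).
- At least 3 points after Cmax, adjusted R² of at least 0.75, linear trapezoidal AUC (Section 11.5.2).

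**Assumed, because not in the documents**
- Single-dose Tmax 1 to 3 h; residual CV 5, 10 and 20%.
- Either one compartment (24 h half-life), or two compartments (2 h and 24 h phases, with 20% or 40% of the weight on the slow phase).

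**Step 1: three-point rule.** After a Cmax at 1 h, the points at 2, 4 and 6 h remain, which is three. After a Cmax at 2 h, only 4 and 6 h remain. So T1/2 is obtainable only when observed Cmax is at 1 h. This needs no model.

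**Step 2: size of the signal.** The true fall from 2 to 6 h is 1 − 0.5^(4/24) = 10.9%. At a half-life of 18 h it is 14.3%, and at 30 h it is 8.8%.

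**Step 3: R² rule.** With n = 3, adjusted R² = 1 − (1 − R²) × 2/1. Requiring 0.75 means R² of at least 0.875 on three points.

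**Step 4: both rules together.** Simulation, 40,000 profiles per setting, true terminal half-life 24 h; entries are for CV 5 / 10 / 20%:

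| Assumed disposition | Day | T1/2 reportable | Median reported T1/2 (h) |
|---|---|---|---|
| One compartment, Tmax 1 h | 1 and 42 | about 24 / 11 / 6% | about 21.5 / 15 / 9.4 |
| One compartment, Tmax 2 h | 1 | 2.4 / 3.1 / 3.0% | 30.7 / 18.5 / 10.2 |
| One compartment, Tmax 2 h | 42 | 10.6 / 6.5 / 4.3% | 24.6 / 16.9 / 10.1 |
| One compartment, Tmax 3 h | 42 | 1.2 / 2.2 / 2.7% | 35.7 / 19.5 / 10.7 |
| Two compartments, 20% slow | 1 | 99.9 / 90 / 54% | 3.4 / 3.4 / 3.3 |
| Two compartments, 40% slow | 42 | 86 / 49 / 20% | 7.7 / 7.4 / 6.1 |

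Reported values are therefore either scarce or, with a fast distribution phase, common but far too short.

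**Step 5: AUCtau.** On Day 1, the part of AUC0-24 lying after 6 h is 71-72% with one compartment and 51-61% with two. It has to be extrapolated on the slope from Steps 1 to 4. On Day 42, setting C(24 h) equal to the pre-dose value gives a linear-trapezoid AUCtau of about 1.01 times the true value with one compartment, and 1.03 to 1.06 times with two. No slope is used.

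**Step 6: which parameters need the slope λz.** T1/2 = ln 2/λz, and Vz/F = (CL/F)/λz, so both need it. At steady state CL/F = dose/AUCtau, which does not. The rule in 11.5.2 therefore withholds a parameter that does not need the slope and omits one that does.

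**Step 7: the alternative half-life.** T1/2,acc = 24 × ln 2 / ln[R/(R − 1)], where R is the accumulation ratio. Without noise, R from AUC0-6h (Day 42 / Day 1) is 2.10 to 2.25 with one compartment and Tmax 1 to 3.6 h, which gives 25.7 to 28.3 h. With two compartments (absorption rate 2 or 4 per h), R is 1.42 to 1.71, which gives about 14 to 19 h. It needs no terminal regression, but it is an effective half-life and should be labelled so.

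**The case against.** The strongest objection is the redaction. The PK row and part of Section 8.7 are hidden, and these are where a later sample or a derivation rule would appear. A reader might take it as stated that sampling stops at 6 h. That is a strong inference from the visible columns and Section 3.1, but it is not a stated fact. This objection stands and makes the estimability conclusion conditional. It does not touch Step 6, nor the mismatch between the definitions list and 11.5.2.

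A reader might also infer that most half-lives cannot be obtained and that those reported will always be short. The documents do not support this, because Tmax, CV and disposition are not given. With two compartments and low noise nearly every profile yields a value. With one compartment, Tmax 2 h and CV 5%, the median is 25 to 31 h, which is not short.

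A further tempting inference is that AUCtau as a whole is compromised. Day 42 has a pre-dose point that resolves it, and no visible text says that AUCtau, or Racc through it, is taken from Day 1.

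Finally, the study is non-confirmatory, dose proportionality is exploratory, and no visible analysis uses T1/2 or Vz/F. The three-point and R² rules already hold back many weak half-lives. All of this is fair. It limits the consequence to the descriptive PK report, and it does not support a claim that dose or interval selection would be misled.

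**Conclusion.** The point holds in two parts.

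First, without any condition: the R² rule in 11.5.2 is wrong as written. It covers CL/F without separating the steady-state case, leaves out Vz/F, and names AUCinf, which is not a listed parameter. The half-life in 11.5.2 and SAP 5.1 also differs from the one in the definitions list.

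Second, conditional on the visible schedule and a half-life near 24 h: terminal T1/2 and Vz/F are not reliably estimable. The half-life is approximate and comes from a contraception clause, but the 2 to 6 h fall stays at 9-14% for any value from 18 to 30 h. The reportable fractions and medians in Step 4 illustrate assumed settings and are not predictions for this drug. A Day 1 AUCtau, if one is derived, shares the problem; Day 42 AUCtau does not, provided the pre-dose value is used.

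The defect is moderate. It affects a secondary objective and can be corrected by wording.

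**What to change.** In Protocol 11.5.2 and SAP 5.1 and 5.3:

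1. Apply the three-point and adjusted R² rules to every slope-dependent parameter (T1/2, Vz/F and any extrapolated AUC). Do not apply them to Day 42 CL/F = dose/AUCtau. Delete AUCinf or add it to the list.
2. Derive AUCtau and CL/F on Day 42, with the pre-dose value as the 24 h point. State how patients whose dose or dosing frequency changed before Day 42 are handled, since Section 6.6 permits alternate-day dosing in Cohort 1 and the substitution assumes a 24 h interval at steady state.
3. Use Cmax and AUC0-6h (AUClast on this grid) for Day 1 exposure, for Racc and for the Day 1 dose-proportionality comparison.
4. Report T1/2,acc as the half-life measure. Drop terminal T1/2 and Vz/F from the list unless the unredacted schedule contains samples late enough to support them.

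The cost is wording only, with no added samples. The downside is that terminal half-life and volume are not reported from this study's non-compartmental analysis. The modelling in Section 11.5.3 should not be counted on to replace them, because it is permitted only for exploring PK/PD relationships.

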5.1 Variables

The following pharmacokinetic parameters will be determined for each analyte using the actual recorded sampling times and non-compartmental method(s) with Phoenix WinNonlin (Version 6.2 or higher): C_{max}, T_{max}, AUC_{last}, AUC_{tau}, R_{acc}, T_{1/2}, V_z/F and CL/F from the plasma concentration-time data.

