5.2 Descriptive analyses

LMB763 and LMB763 metabolites ^{Corporate Confidential Information} plasma concentrations will be listed by treatment, subject, and visit/sampling time point. Descriptive summary statistics will be provided by treatment and visit/sampling time point. Summary statistics will include mean (arithmetic and geometric), SD, CV (arithmetic and geometric), median, minimum, maximum, and the frequency (n, %) of concentrations below the LLOQ. Concentrations below LLOQ will be treated as zero in summary statistics and for PK parameter calculations. A geometric mean will not be reported if the dataset includes zero values. Graphical methods will be employed to show mean and individual concentration-time profiles.

Pharmacokinetic parameters will be listed by treatment and subject and summarized by treatment with descriptive statistics as listed above. Since T_{max} is generally evaluated by a nonparametric method, only median, minimum, and maximum will be reported.

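### The terminal-fit rule in Protocol 11.5.2 withholds T1/2, AUCinf and CL/F but does not name Vz/F, which uses the same slope

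*Protocol*

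**What the plan says.** Protocol 11.5.2 names Cmax, Tmax, AUClast and AUCtau, and then "Racc, T1/2, Vz/F and CL/F from the plasma concentration-time data". Two conditions on the terminal regression follow. The first is a minimum size: the regression "for the determination of T1/2 will include at least 3 data points after Cmax". The second is a fit criterion: if adjusted R² is below 0.75, "no values will be reported for T1/2, AUCinf and CL/F".

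The protocol's list of pharmacokinetic definitions describes Vz/F as "The apparent volume of distribution during the terminal elimination phase following extravascular administration". It has no entry for AUCinf.

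SAP 5.1 repeats the same eight parameters and asks for them for each analyte; AUCinf is again absent. SAP 5.2 covers "LMB763 and LMB763 metabolites" and adds: "Pharmacokinetic parameters will be listed by treatment and subject and summarized by treatment with descriptive statistics as listed above". The unredacted text of SAP 5.1 to 5.3 gives no minimum number of points, no R² cutoff and no withholding rule. SAP section 2 includes summary statistics for PK parameters in the first interpretable results.

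**The concern.** A rule that discards parameters resting on a poor terminal fit should cover all the parameters that rest on it. This one is an explicit list that does not match the list of parameters to be calculated. It names one parameter that is not planned in the unredacted text (AUCinf) and omits one that is planned (Vz/F).

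A programmer who implements the sentence as written would blank T1/2 and CL/F for a failing profile and still output Vz/F. That value would then enter the listings and the summary statistics, carrying the slope error that the rule is meant to screen out. For metabolites the position is less clear still, because Protocol 11.5.2 speaks only of LMB763.

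**Working it through.** **The lists side by side (unredacted text)**

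| Parameter | Protocol definitions | Protocol 11.5.2 list | SAP 5.1 list | Withheld by the rule |
|---|---|---|---|---|
| Vz/F | yes | yes | yes | no |
| CL/F | yes | yes | yes | yes |
| AUCinf | no | no | no | yes |

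Elsewhere, the secondary-objective tables say only AUC, and the PK/PD sections of both documents name AUCtau.

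**Dependence of Vz/F on the slope.** Write λz for the terminal slope. The standard identities are T1/2 = ln 2 / λz and Vz/F = (CL/F) / λz = (CL/F) × T1/2 / ln 2. With an illustrative CL/F of 0.1 (assumed, arbitrary units):

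| λz | T1/2 | Vz/F |
|---|---|---|
| 0.02 | 34.66 | 5.0 |
| 0.04 | 17.33 | 2.5 |
| 0.08 | 8.66 | 1.25 |

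Halving the slope doubles both T1/2 and Vz/F. This exact proportionality holds when CL/F itself does not use the slope. If instead CL/F = dose/AUCinf with AUCinf = AUClast + Clast/λz (observed Clast), then Vz/F = dose / (λz × AUClast + Clast). The slope still enters, but its relative error is damped by about the ratio AUClast/AUCinf. Vz/F depends on the slope either way.

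**How poor a slope at the cutoff is.** The inputs are the 0.75 cutoff and the three-point minimum, both from Protocol 11.5.2. For n points:

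- R² = 1 − (1 − 0.75)(n − 2)/(n − 1)
- t² = (n − 2)R² / (1 − R²) = 3n − 2
- relative SE of the slope = 1/√(3n − 2)

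| n | R² | t | Relative SE | Two-sided p |
|---|---|---|---|---|
| 3 | 0.875 | √7 = 2.646 | 38% | 0.230 |
| 4 | 0.833 | √10 = 3.162 | 32% | 0.087 |
| 5 | 0.8125 | √13 = 3.606 | 28% | 0.037 |
| 6 | 0.800 | √16 = 4.000 | 25% | 0.016 |

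A profile that fails the criterion has a larger relative SE than the figure for its own n. With 3 or 4 points, a failing slope has a 95% confidence interval that includes zero. T1/2 then has no finite upper limit, nor does Vz/F when CL/F does not use the slope. None of these figures needs the sampling schedule. The plan states no figure of its own on this point to reproduce.

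**The case against.** The strongest reply is that Vz/F is the product of two withheld quantities, CL/F and T1/2, divided by ln 2, so a pharmacokineticist would drop it without being told. That is probably what was intended. But the rule is an enumerated list, and nothing in it extends to derived quantities. A sensible analyst may get this right; the text does not require it.

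Three further replies stand in part. Protocol 11.5.2 refers to Section 8.7 for the calculations, and part of 8.7 is redacted, so AUCinf may be planned there. SAP 1.1 says that the SAP implements the protocol's analysis, so its silence does not switch the rule off for LMB763; only metabolites are left uncovered. The three-point minimum is worded for T1/2, but the same regression supplies the slope for Vz/F, so little hangs on that wording.

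A reader might infer two stronger points that the documents do not support:

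- **That the rule withholds CL/F needlessly**, because dose/AUCtau at steady state needs no terminal slope. The CL/F method may stand in redacted 8.7, and AUCtau may itself need extrapolation. In a one-compartment model with a 24 h half-life, an assumed absorption rate of 1.5 to 5/h and no sample after 6 h, about 69% of the 24 h AUCtau lies after 6 h.
- **That most profiles must fail**, because the visible Day 1 and Day 42 columns end at 6 h and exclusion criterion 9 implies a half-life of about 5 days / 5 = 24 h. The PK rows are redacted, so the last sampling time is unknown. Absorption rate and residual variation would also have to be assumed. Even on those assumptions (absorption rate 3 to 5/h), the harm is not clear-cut. At residual CVs of 5%, 10% and 20%, Vz/F is off by more than twofold in 34-39%, 40-41% and 51-52% of failing profiles, against 12-13%, 32-36% and 67-69% of passing ones. At 20% the values that pass are worse.

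The bound in the table also compares slopes only at equal n. A just-failing six-point slope (about 25%) is more precise than a just-passing three-point slope (38%).

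**Conclusion.** The mismatch is real and can be read from unredacted text: Vz/F is listed, defined on the terminal phase and omitted from the rule, while AUCinf is in the rule and in no unredacted list. As written, Vz/F may be reported from a slope rejected for T1/2, with a relative SE above 38%, 32%, 28% or 25% for 3, 4, 5 or 6 points. This rests on the standard definition of Vz/F and on ordinary least squares for the terminal regression. It needs no assumption about sampling times or absorption.

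Severity is minor. These are descriptive secondary parameters; no hypothesis test or stated decision uses T1/2 or Vz/F, and the ALT analysis and power are unaffected. How many profiles would be affected cannot be determined from the documents.

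**What to change.** In Protocol 11.5.2, replace the withholding sentence with wording to this effect: *When fewer than three post-Cmax points are available, or the terminal regression's adjusted R² is under 0.75, T1/2, Vz/F and any other parameter that uses the terminal slope are not reported; this includes CL/F, and AUCtau if it is extrapolated with that slope.* Add no blanket exemption for CL/F, since one could release slope-dependent values.

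Either delete AUCinf or add it to the parameter list, the definitions and SAP 5.1.

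State in SAP 5.1 that the rule applies to every analyte, including metabolites. In SAP 5.2, show by treatment, day and analyte how many profiles gave a reportable value out of those with PK data.

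The cost is wording in two documents and no extra samples. There will be fewer Vz/F values, and those that pass are a selected set. The count of reportable profiles lets the reader see how selected.
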